6.7.8 Exploratory Efficacy Analysis: 6MWT

% Predicted of Normal 6MWT Distance

The 6MWT performance of subjects relative to peers will be evaluated as a sensitivity analysis using % of predicted normal 6MWT distance values. Predicted normal values will be calculated as described in [section 6.5.2](#). Percent of predicted normal 6MWT distance achieved for the 12g/day SA-ER/SA-IR treatment group at each study time point will be evaluated using descriptive statistics for Part II UX001-CL201.

A GEE Model similar in construct to that performed for the 6MWT efficacy variable will be completed for the % predicted of Normal 6MWT.

In addition the cross-over treatment pathway groups may be compared with the change observed in prior treatment period for the % predicted of normal 6MWT distance. Trends in the change observed in % predicted of normal 6MWT distance will be displayed using graphical techniques.

6.7.9 Efficacy Analysis: Walking Speed Test

Gait Speed – Comfortable and Maximum Pace:

The gait speed test will be used to evaluate walking speed at a comfortable and maximum pace on a 7.62 meter (25 feet) course. The speed at which the subject can walk 7.62 meters will be measured in centimeters/second (cm/s) for the comfortable and maximum paces. Comfortable gait speed (CGS) and maximum gait speed (MGS) observed for the 12g/day SA-ER/SA-IR treatment group in Part II of UX001-CL202 will be evaluated using descriptive statistics.

A GEE analysis model will be developed to examine the change in speed (cm/s) at the comfortable pace (CGS) for the 6-month Part II analysis with study time points as categorical predictors and age, height and Baseline CGS as covariates. The same GEE model will be used to assess change in speed (cm/s) at maximum pace (MGS). The defined baselines and planned comparisons to be examined in this analysis are identified in [Table 8](#).

In addition the cross-over treatment pathway groups may be compared with the change observed in prior treatment period for the CGS and MGS parameters. Trends in the change observed in the CGS and MGS parameters will be displayed using graphical techniques.

6.7.10 Exploratory Efficacy Analysis: Walking Speed Test

% Predicted of Normal Gait Speed – Comfortable and Maximum Pace

The gait speed of subjects relative to peers will be evaluated as a sensitivity analysis using % of height-normalized predicted speed values for CGS and MGS parameters. Predicted normal values will be calculated as described in [section 6.5.2](#). Percent of predicted normal

CGS and MGS observed for the 12g/day SA-ER/SA-IR treatment group in Part II of UX001-CL202 at each study time point will be summarized using descriptive statistics.

GEE models similar to those performed for the CGS and MGS parameters will be completed as sensitivity analyses.

In addition the cross-over treatment pathway groups may be compared with the change observed in prior treatment period for the % predicted CGS and MGS parameters. Trends in the change observed in the % predicted CGS and MGS parameters will be displayed using graphical techniques.

6.7.11 Efficacy Analysis: Weighted Arm Lift Test

The weighted arm lift test will be used to assess the ability to raise a weighted object overhead with each arm. Performance will be measured by the number of times that a subject can lift a 1 kg dumbbell overhead in a 30-second period. The test will be performed twice, once with the left arm and once with the right arm. The number of repetitions performed on each side for the 12g/day SA-ER/SA-IR treatment group at each study time point will be evaluated using descriptive statistics on the average result of the left and right side.

A GEE analysis model will be developed to examine the change in weighted arm lift test for the 6-month Part II analysis with study time points as categorical predictors and gender, age, and baseline weighted arm lift as covariates. Baseline for these analysis will be the week 48 observation (termination visit) from UX001-CL201. The comparisons to be examined are identified in [Table 8](#).

In addition the cross-over treatment pathway groups may be compared with the change observed in prior treatment period for weighted arm lift test. Trends in the change observed in the weighted arm lift test will be displayed using graphical techniques.

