6.5.8 Determination of Baseline Values

Multiple baseline values for efficacy endpoints will be considered for the planned analyses. [Figure 1](#) presents an analysis map that highlights the various possible baselines for planned analyses. [Table 3](#) presents a dosing pathway matrix for all subjects enrolled in the study. Each pathway can be associated with a different baseline for analysis summaries and comparisons.

In order to examine the long term trends and changes in SA therapy for those subjects who roll-over from UX001-CL201 additional analyses will also be performed using baseline assessments obtained at the following time points ([Figure 1](#)):

- UX001-CL201 6/6 and 3/3 rollover subjects: UX001-CL201 Week 0 Visit
- UX001-CL201 0/6 and 0/3 rollover subjects: UX001-CL201 Week 24 Visit
- UX001-CL201 0/6 + 6/6 rollover subjects: UX001-CL201 Week 48 Visit
- UX001-CL201 0/3 + 3/3 rollover subjects: UX001-CL201 Week 48 Visit
- UX001-CL201 All rollover subjects: UX001-CL201 Week 48 Visit

- UX001-CL201 All rollover subjects: UX001-CL202 Part I Termination Visit
- UX001-CL202 Treatment Naïve Subjects: UX001-CL202 Part II Screening/Baseline Visit (Week 0: Note that protocol refers to this as week 12 on the T&E schedule.)

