6.7 Statistical Analysis: Clinical Efficacy

6.7.1 Planned Comparisons for Clinical Efficacy Parameters

The planned comparisons for UX001-CL202 are based on change from baseline assessments, where different baselines are utilized to evaluate treatment across a subject's treatment in

both UX001-CL201 and UX001-CL202. [Table 8](#) presents the planned comparisons for study data obtained in UX001-CL202 compared with study data from UX001-CL201 for roll-over subjects, as well as the treatment naïve subjects in UX001-CL202.

Clinical efficacy data collected in Part I of UX001-CL202 (all roll-over subjects dosed with 6g/day SA-ER) will not be included in planned comparisons for the clinical efficacy analysis.

Additional comparisons not specified in this statistical analysis plan may be completed as prospective analyses are completed to better understand study results. These additional comparisons will be clearly identified in final reporting.

Table 8 Planned Comparisons

Planned Comparison	Description
Primary Analysis #1: Week 24 12g/day SA/ER/SA-IR vs. Week 0	All subjects who roll-over from UX001CL201 will have their week 0 assigned as baseline (Part I termination visit of the 202 study) and the change from this score will be compared to the week 24 12g/day SA-ER/SA-IR treatment to assess the impact of the 12g/day SA-ER/SA-IR dose.
Primary Analysis #2: Week 24 12g/day SA/ER/SA-IR vs. Week 48 UX001-CL201 for 6/6+0/6 SA-ER	All subjects who roll-over from UX001CL201 will have their week 48 assigned as baseline and the change from this score will be compared to the week 24 12g/day SA-ER/SA-IR treatment to assess the impact of the 12g/day SA-ER/SA-IR dose across the combined 6/6+0/6 dose (UX001-CL201 subjects treated with 0/6 or 6/6 SA-ER will be combined for comparison from dosing pathways 1 and 3 from Table 3). A second comparison will be with a 6 minute walk test at Screening of ≥ 200 m (6MWT ≥ 200 m)
Primary Analysis #3: Week 24 12g/day SA/ER/SA-IR vs. Week 48 UX001-CL201 for 3/3+0/3	All subjects who roll-over from UX001CL201 will have their week 48 assigned as baseline and

Planned Comparison	Description

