SA-ER	
the change from this score will be compared to the week 24 12g/day SA-ER/SA-IR treatment to assess the impact of the 12g/day SA-ER/SA-IR dose across the combined 3/3+0/3 dose (UX001-CL201 subjects treated with 0/3 or 3/3 SA-ER will be combined for comparison from dosing pathways 2 and 4 from Table 3)
 
A second comparison will be with a 6 minute walk test at Screening of ≥ 200 m (6MWT≥ 200m)

Secondary Analysis: Stability in endpoint over time and dose from Week 0 UX001-CL201 through Week 24 UX001-CL202. (Trend over time)
	
All subjects who roll-over from UX001CL201 will have their week 0 assigned as baseline and the stability from this baseline score will be assessed over time through the week 24 12g/day SA-ER/SA-IR treatment to assess the impact of dose combinations over time. For this analysis the UX001-CL201 subjects treated with 0/6 or 6/6 SA-ER will be combined for analysis from dosing pathways 1 and 3 and subjects treated with 0/3 or 3/3 SA-ER will be combined for analysis from dosing pathways 2 and 4 (Table 3). Each dosing pathway combination will be a separate analysis to assess the trend in endpoint scores over time and dose.
 
A second comparison will be with a 6 minute walk test at Screening of ≥ 200 m (6MWT≥ 200m)

Treatment Naïve Primary Analysis: Week 24 12g/day SA/ER/SA-IR vs. Week 0 Baseline (Week 12 on T&E)
	
Treatment Naïve subjects who enroll in UX001-CL202 will have a primary comparison of their change from baseline assessment for efficacy parameters.

Treatment Naïve Secondary Analysis: Week 24 12g/day SA/ER/SA-IR vs.
	
Treatment Naïve subjects in UX001-CL202

Planned Comparison	Description
Week 0-24 UX001-CL201 Placebo	endpoint data from week 0 to 24 will be compared to the UX001-CL201 Placebo (for those patients with 6MWT >=200m) treated subjects' endpoint data from week 0 to 24 for change from baseline assessments.

Additional comparisons may be defined upon review of the data to examine trends throughout a subject's treatment course through both UX001-CL201 and UX001-CL202, via the dosing pathways identified in [Table 3](#) and [Figure 1](#).

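### SAP 6.7.11 to 6.7.13 name CL201 Week 48 as the only baseline for arm lift, HIBM-FAS and CK, but four of the six Table 8 comparisons they apply use a different baseline

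*SAP*

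**What the plan says.** SAP 6.7.11 (weighted arm lift), 6.7.12 (HIBM-FAS total, with the approach repeated for three subscales) and 6.7.13 (CK) contain the same sentence: "Baseline for these analysis will be the week 48 observation (termination visit) from UX001-CL201". Each section then refers to Table 8 for the comparisons.

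Table 8 (SAP 6.7.1) sets the baseline row by row:

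- Primary Analysis #1: "All subjects who roll-over from UX001CL201 will have their week 0 assigned as baseline (Part I termination visit of the 202 study".
- Primary Analysis #2: "All subjects who roll-over from UX001CL201 will have their week 48 assigned as baseline and the change from this score will be compared".
- Primary Analysis #3 is labelled "Primary Analysis #3: Week 24 12g/day SA/ER/SA-IR vs. Week 48 UX001-CL201 for 3/3+0/3" and also uses Week 48.
- Secondary Analysis: "All subjects who roll-over from UX001CL201 will have their week 0 assigned as baseline and the stability from this baseline score will be assessed". The row title places this Week 0 in CL201.
- Treatment Naïve Primary: these subjects "will have a primary comparison of their change from baseline assessment for efficacy parameters", with Week 0 as that baseline.
- Treatment Naïve Secondary compares Weeks 0 to 24 in naïve subjects with Weeks 0 to 24 in the CL201 placebo subjects.

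SAP 6.5.8 lists several baselines, among them "UX001-CL202 Treatment Naïve Subjects: UX001-CL202 Part II Screening/Baseline Visit". SAP 5.4 says that the baseline for each change-from-baseline comparison is given with the specific analysis. The 6MWT and gait speed sections (6.7.7 and 6.7.9) take their baselines from Table 8 and name no single visit.

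**The concern.** SAP 5.4 leaves the choice of baseline to the individual analysis sections, so the Week 48 sentence is an operative instruction and not background. One programmer following 6.7.11 to 6.7.13 and another following Table 8 would produce different results for the same table.

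The literal rule fails differently by row. In Primary #1 it puts Part I treatment at 6 g/day inside a change meant to show the effect of 12 g/day. It also departs from Protocol 7.6.1.1, which measures continuing subjects from the Part II baseline to Month 6. In the Secondary trend and in the placebo arm of Naïve Secondary, the baseline comes after data that it is supposed to precede. For naïve subjects no such value exists. Primary #1 would also start from a different visit for arm lift, FAS and CK than for 6MWT and gait speed. With two candidate baselines and no rule of precedence, the choice could be made after the data are seen.

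**Working it through.** The plan gives no figure to reproduce. The check matches baselines row by row and then counts tables.

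**Step 1. Table 8 against the Week 48 sentence.** Tables per endpoint are counted from the list in SAP 8.1.

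| Table 8 row | Baseline in Table 8 | Week 48? | Tables per endpoint |
|---|---|---|---|
| Primary #1 | CL202 Part I Termination Visit | No | 2 |
| Primary #2 | CL201 Week 48 | Yes | 2 |
| Primary #3 | CL201 Week 48 | Yes | 2 |
| Secondary | CL201 Week 0 | No | 2 |
| Naïve Primary | Own Week 0 in CL202 | No | 1 |
| Naïve Secondary | Week 0 in each study | No | 2 |

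Four of six rows conflict. Among the four rollover rows, two conflict.

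**Step 2. Planned tables affected.** Table IDs are 231–242 (arm lift, 12), 435–482 (FAS, 48) and 495–506 (CK, 12).

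- Total: 12 + 48 + 12 = 72. At 12 tables per endpoint, that is 6 endpoints.
- Less one summary table each: 72 − 6 = 66 comparison tables.
- In conflict per endpoint: 2 + 2 + 1 + 2 = 7. Over six endpoints: 7 × 6 = 42, and 42/66 = 64%.
- Naïve tables: (1 + 2) × 6 = 18. The other 24 are 12 for Primary #1 and 12 for the Secondary trend.

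**Step 3. Primary #1 read literally.** Let p be a subject's weeks in Part I, up to about 12 (Protocol synopsis and 7.4.3). The change runs over p + 24 weeks, of which p are on 6 g/day, so the share is p/(p + 24).

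- p = 12: 12/36 = 33%.
- p = 6 (illustrative): 6/30 = 20%.
- p = 0: 0/24 = 0%.

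The note to SAP Figure 1 says that time in Part I varied and that some rollover subjects went straight to Part II. One third is therefore a ceiling. For subjects with p = 0 the two baselines may coincide.

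**Step 4. Order of baseline and outcome.** The Secondary trend starts at CL201 Week 0 and ends at Part II Week 24. A Week 48 baseline has 48 weeks of that trend before it. The placebo comparator in Naïve Secondary is observed over Weeks 0 to 24, so Week 48 falls 24 weeks after its whole outcome window. By then Table 3 has those subjects on 3 or 6 g/day.

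**Step 5. Naïve subjects.** Table 3 (pathway 5) shows no CL201 treatment for them, so none of the roughly 10 of 56 planned subjects (18%) has a CL201 Week 48 value. Three places do give their baseline: SAP 6.5.8, the naïve rows of Table 8 and, for CK, the first paragraph of 6.7.13.

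**The case against.** The best defence is that the intent can be recovered. SAP 6.5.8 expects several baselines, Table 8 states one for each row, and a sentence about CL201 Week 48 cannot apply to people who were never in CL201. For naïve subjects this stands. A reader might infer that the 18 naïve tables cannot be computed, but the documents do not support that: the baseline is defined elsewhere, and the Week 48 sentence contradicts it. For rollover subjects the defence is weaker, because a Week 48 value should exist and SAP 5.4 gives force to the section-level text.

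The sentence might instead be read as defining only the baseline covariate. The conflict would remain: the covariate would be absent for naïve subjects and later than the outcome for the placebo comparator.

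A reader might also infer that the strength-against-function analyses in SAP 6.8 would relate changes over different periods. Those sections set no baseline, do not refer back to 6.7.11 to 6.7.13, and are framed as Part II analyses, so the text does not establish this.

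Two further points stand. Primary #2 and #3 include Part I time for every endpoint by design, so that feature is not peculiar to this sentence and remains after the fix. The other endpoints are not perfectly uniform either: 6.7.7 names the Screening 6MWT distance as covariate while taking the baseline for change from Table 8.

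**Conclusion.** The contradiction is real. The Week 48 sentence is right for Primary #2 and #3 and wrong for the other four Table 8 rows, which account for 42 of 66 comparison tables over six endpoints. The worst literal result is a baseline that follows the outcome, in the Secondary trend and the Naïve Secondary placebo comparator. In Primary #1 the effect is to include Part I time, at most about one third of the interval and nothing for some subjects.

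The counts rest on the SAP 8.1 list. The one-third figure assumes a full 12 weeks in Part I.

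This should be fixed, but a must-fix rating would go too far. The study is open-label and not powered for comparisons, CK is exploratory, the naïve baseline is recoverable, and the HHD, 6MWT and gait speed sections do not carry the sentence.

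**What to change.** In SAP 6.7.11, 6.7.12 and 6.7.13, replace the Week 48 sentence with the approach of 6.7.7 and 6.7.9. For example: *Baseline for each comparison is the visit assigned to it in Table 8; the same value enters the model as the baseline covariate.* Then state the assignments:

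- Primary #1: Part I Termination Visit (the Part II baseline). For rollover subjects who went directly to Part II, the last assessment before the first Part II dose.
- Primary #2 and #3: CL201 Week 48.
- Secondary trend: CL201 Week 0.
- Naïve subjects, both rows: Part II Screening/Baseline.
- Placebo comparator in Naïve Secondary: CL201 Week 0.

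Protocol 7.2 reports that the 6-month analysis has been done, and SAP 6.3 calls that analysis primary for clinical efficacy. The study report should therefore state which baseline was used for these six endpoints. Where it was not the Table 8 baseline, the affected tables should be rerun and labelled as such.

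The cost is one sentence in three sections, the list above, and a check of the completed outputs. No new data are needed: arm lift, HIBM-FAS and CK are scheduled at the Part I Termination and Part II Screening/Baseline visits. The CL201 Week 0 values are assumed to exist, as Table 8 itself assumes. Sample size and alpha do not change.

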6.7.12 Efficacy Analysis: HIBM Functional Activities Scale

The HIBM-FAS will be administered to assess subject's self-reported activity limitations resulting from HIBM. Activity limitation will be measured with a total score and 3 subscale scores for mobility, upper extremity function and self-care. The individual HIBM variables are presented in [Table 6](#). Total and subscale scores will be calculated as described in [Section 6.5.2](#). Total and subscale scores will be evaluated for the 12g/day SA-ER/SA-IR dose at each study time point in Part II of UX001-CL202 using descriptive statistics.

A GEE analysis model will be developed to examine the change in HIBM-FAS with study time points as categorical predictors and gender, age, and baseline as covariates. Baseline for these analysis will be the week 48 observation (termination visit) from UX001-CL201. The comparisons to be examined are identified in [Table 8](#). The GEE approach detailed above for

the analysis of the HIBM-FAS total score will be repeated for HIBM-FAS Mobility, Upper Extremity and Self-Care subscales.

In addition the cross-over treatment pathway groups may be compared with the change observed in prior treatment period for HIBM-FAS total score, as well as the individual scores for HIBM-FAS Mobility, Upper Extremity and Self-Care subscales. Trends in the change observed in the HIBM-FAS will be displayed using graphical techniques.

6.7.13 Exploratory Efficacy Analysis: Creatine Kinase

Creatine kinase (CK) samples are being assessed at baseline and the Part I termination visit, and at months 1, 3, 6, 12, 24, 36, and the termination visit in Part II in UX001-CL202 for subjects who roll-over from UX001-CL201. Treatment Naïve subjects who are enrolled in Part II of this study will have a baseline assessed at the screening visit.

Changes in CK will be evaluated using descriptive and graphical summaries to evaluate change over time in CK levels after dosing with 12g/day SA-ER/SA-IR in Part II.

A GEE analysis model will be developed to examine the change in creatine kinase for the 6-month Part II analysis with study time points, dose, and baseline creatine kinase as covariates. Baseline for these analysis will be the week 48 observation (termination visit) from UX001-CL201. The comparisons to be examined are identified in [Table 8](#).

6.8 Statistical Analysis: Effect of Changes in Muscle Strength, PROs, and Physical Function

6.8.1 Upper Extremity Muscle Strength vs. Weighted Arm Lift Test

GEE will be used to assess the relationship between changes in upper extremity muscle strength and changes in arm raising ability. Changes in HHD UE composite scores will be compared to changes in the number of repetitions performed in the weighted arm lift test. The GEE will be performed with and without treatment in the model for Part II in UX001-CL202. Additional comparisons may be made to explore the changes in these muscle strength parameters over the dosing pathways identified in [Table 3](#) and in [Table 8](#).

6.8.2 Lower Extremity Muscle Strength vs. 6MWT Distance

GEE will be used to assess the relationship between changes in lower extremity muscle strength and changes in the results for the 6-minute walk test (6MWT). Changes in HHD LE composite scores will be compared to changes in the 6MWT distance (as measured in meters). The GEE will be performed with and without treatment in the model for Part II in

UX001-CL202. Additional comparisons may be made to explore the changes in these muscle strength parameters over the dosing pathways identified in [Table 3](#) and in [Table 8](#).

6.8.3 Lower Extremity Muscle Strength vs. Gait Speed Test

GEE will be used to assess the relationship between changes in lower extremity muscle strength and changes in the results for the comfortable gait speed (CGS) and maximum gait speed (MGS) observed for the 12g/day SA-ER/SA-IR treatment group in Part II of UX001-CL202. The GEE will be performed with and without treatment in the model for Part II in UX001-CL202 to examine changes in HHD LE composite scores compared to changes in CGS and MGS (as measured in cm/s). Additional comparisons may be made to explore the changes in these muscle strength parameters over the dosing pathways identified in [Table 3](#) and in [Table 8](#).

6.8.4 HIBM-FAS Total and UE Subscale Score vs. HHD UE Composite Score

GEE will be used to assess the relationship between changes in self-reported functional disability and changes in upper extremity strength. Changes in HIBM-FAS total and HIBM-FAS UE subscale score will be compared to changes in HHD UE composite score. The GEE will be performed with and without treatment in the model for Part II in UX001-CL202. Additional comparisons may be made to explore the changes in these parameters over the dosing pathways identified in [Table 3](#) and in [Table 8](#).

6.8.5 HIBM-FAS Total and Mobility Subscale Score vs. HHD LE Composite Score

GEE will be used to assess the relationship between changes in self-reported functional disability and changes in lower extremity strength. Changes in HIBM-FAS total and HIBM-FAS Mobility subscale score will be compared to changes in HHD LE composite score. The GEE will be performed with and without treatment in the model for Part II in UX001-CL202. Additional comparisons may be made to explore the changes in these parameters over the dosing pathways identified in [Table 3](#) and in [Table 8](#).

